5.2 Pharmacokinetic properties

Absorption:

Atorvastatin is rapidly absorbed after oral administration; maximum plasma concentrations (Cmax) occur within 1 to 2

hours. Extent of absorption increases in proportion to atorvastatin dose. After oral administration, atorvastatin film-coated

tablets are 95% to 99% bioavailable compared to the oral solution. The absolute bioavailability of atorvastatin is

approximately 12% and the systemic availability of

HMG-CoA reductase inhibitory activity is approximately 30%. The low systemic availability is attributed to presystemic

clearance in gastrointestinal mucosa and/or hepatic first-pass metabolism. Distribution:

Mean volume of distribution of atorvastatin is approximately 381 I.

Atorvastatin is ≥ 98% bound to plasma proteins.

Biotransformation:

Atorvastatin is metabolised by cytochrome P450 3A4 to ortho- and parahydroxylated derivatives and various betaoxidation

products. Apart from other pathways these products are further metabolized via glucuronidation. In vitro,

inhibition of HMG-CoA reductase by ortho- and parahydroxylated metabolites is equivalent to that of atorvastatin.

Approximately 70% of circulating inhibitory activity for HMG-CoA reductase is attributed to active metabolites.

Elimination:

Atorvastatin is eliminated primarily in bile following hepatic and/or extrahepatic metabolism. However, the atorvastatin does not appear to undergo significant enterohepatic recirculation. Mean plasma elimination half-life of atorvastatin in

Confidential Page 57 of 22

Version 1.4 10th April 2020

humans is approximately 14 hours. The half-life of inhibitory activity for HMG-CoA reductase is approximately 20 to 30

hours due to the contribution of active metabolites.

Atorvastatin is a substrate of the hepatic transporters, organic anion-transporting polypeptide 1B1 (OATP1B1) and 1B3

(OATP1B3) transporter. Metabolites of atorvastatin are substrates of

OATP1B1. Atorvastatin is also identified as a

substrate of the efflux transporters multi-drug resistance protein 1 (MDR1) and breast cancer resistance protein (BCRP),

which may limit the intestinal absorption and biliary clearance of atorvastatin.

Special Populations

Elderly: Plasma concentrations of atorvastatin and its active metabolotes are higher in healthy elderly subjects than in

young adults while the lipid effects were comparable to those seen in younger patient populations.

Paediatric: In an open-label, 8-week study, Tanner Stage 1 (N=15) and Tanner Stage ≥ 2 (N=24) paediatric patients

(ages 6-17 years) with heterozygous familial hyper-cholesterolemia and baseline LDL-C \geq 4 mmol/L were treated with 5

or 10 mg of chewable or 10 or 20 mg of film-coated atorvastatin tablets once daily, respectively. Body weight was the

only significant covariate in atorvastatin population PK model. Apparent oral clearance of atorvastatin in paediatric

subjects appeared similar to adults when scaled allometrically by body weight. Consistent decreases in LDL-C and TC

were observed over the range of atorvastatin and o-hydroxyatorvastatin exposures.

Gender: Concentrations of atorvastatin and its active metabolites in women differ from those in men (women:

approximately 20% higher for Cmax and 10% lower for AUC). These differences were of no clinical significance,

resulting in no clinically significant differences in lipid effects among men and women.

Renal Insufficiency: Renal disease has no influence on the plasma concentrations or lipid effects of atorvastatin and its active metabolites.

Hepatic Insufficiency: Plasma concentrations of atorvastatin and its active metabolites are markedly increased

(approximately 16-fold in Cmax and approx.11-fold in AUC) in patients with chronic alcoholic liver disease (Child-Pugh B).

SLOC1B1 polymorphism: Hepatic uptake of all HMG-CoA reductase inhibitors including atorvastatin, involves the

OATP1B1 transporter. In patients with SLCO1B1 polymorphism there is a risk of increased exposure of atorvastatin,

Confidential Page 58 of 22

Version 1.4 10th April 2020

which may lead to an increased risk of rhabdomyolysis (see section 4.4). Polymorphism in the gene encoding OATP1B1

(SLCO1B1 c.521CC) is associated with a 2.4-fold higher atorvastatin exposure (AUC) than in individuals without this

genotype variant (c.521TT). A genetically impaired hepatic uptake of atorvastatin is also possible in these patients.

Possible consequences for the efficacy are unknown.

5.3 Preclinical safety data

Atorvastatin was negative for mutagenic and clastogenic potential in a battery of 4 in vitro tests and 1 in vivo assay.

Atorvastatin was not found to be carcinogenic in rats, but high doses in mice (resulting in 6-11 fold the AUC0-24h

reached in humans at the highest recommended dose) showed hepatocellular adenomas in males and hepatocellular carcinomas in females.

There is evidence from animal experimental studies that HMG-CoA reductase inhibitors may affect the development of

embryos or fetuses. In rats, rabbits and dogs atorvastatin had no effect on fertility and was not teratogenic; however, at

maternally toxic doses fetal toxicity was observed in rats and rabbits. The development of the rat offspring was delayed

and post-natal survival reduced during exposure of the dams to high doses of atorvastatin. In rats, there is evidence of

placental transfer. In rats, plasma concentrations of atorvastatin are similar to those in milk. It is not known whether

atorvastatin or its metabolites are excreted in human milk.

6. Pharmaceutical particulars

6.1 List of excipients

Tablet core:

Microcrystalline cellulose

Lactose monohydrate

Colloidal anhydrous silica

Croscarmellose sodium

Sodium hydrogen carbonate

Sodium carbonate, anhydrous

Hydroxypropylcellulose

Magnesium stearate

Butylhydroxyanisole

Butylhydroxytoluene

Tablet coating:

Opadry YS-1-7040 white

Hypromellose

Macrogol 8000

Titanium dioxide (E171)

Talc

6.2 Incompatibilities

Confidential Page 59 of 22

Version 1.4 10th April 2020

Not applicable.

6.3 Shelf life

24 months

6.4 Special precautions for storage

Store below 25°C

6.5 Nature and contents of container

Cold form blister laminate (structure: oriented polyamide/ aluminium foil/

PVC) with the backing of hard tempered,

aluminium foil coated with heat seal lacquer on inner side

Packs of 10, 14, 20, 28, 30, 50, 56, 60, 84, 90, 98, 100 film-coated tablets each

(Not all pack size may be marketed)

Peter Greven Nederland C.V.

[name] Industrial Nr. 4625

[contact] [contact]

STATEMENT

Company	To whom it may concern				
То	To whom it may concern	Designation	E-Mail		
From	[name]	Date	July 26, 2013		

Subject: Declaration concerning BSE/TSE

Name of Material: LIGAMED MF-2-V (Magnesium Stearate)

We hereby declare that above-mentioned material for use in food, drugs and medical application are not manufactured of fatty acid of animal origin but only fatty acid of 100% vegetable origin is used. The stearic acid, which is used, is derived from palm oil and is originated in Malaysia. Furthermore in our production facility in Venlo are only fatty acids used based on vegetable origin. Also during the process the material does not come in contact with any animal derived products. As a consequence the EU directive 1999/82/EEC, CPMP Note fore Guidance and EMEA (European Medicines Agency) regulation 410-01 rev. 3 is not applicable.

[name] QA-Assistant Peter Greven Nederland C.V.

Venlo, July 26, 2013

Page 1 of 1

Confidential Page 64 of 22

SAMSON Protocol No: 1.4

Version 1.4 10th April 2020

An die interessierte Partei / To whom it may concern

[name] Quality Unit / Regulatory Affairs

Date of issue: 18.11.2015 Page 1/1 Doc.-No. EIP-1003 Revision 5

TSE / BSE-Statement

Meggle

- Lactose Monohydrate Ph. Eur. / USP-NF / JP: CapsuLac® 60, FlowLac® 90, FlowLac® 100, GranuLac® 70, GranuLac® 140, GranuLac® 200, GranuLac® 230, PrismaLac® 40, SacheLac® 80, SorboLac® 400, SpheroLac® 100, Tablettose® 70, Tablettose® 70, Tablettose® 80, Inhalac® 230, Inhalac® 230, Inhalac® 250, Inh
- InhaLac® 251, InhaLac® 400, Lactose monohydrate Low Endotoxin
- Anhydrous Lactose Monohydrate USP-NF / Ph. Eur. / JP: DuraLac® H

This statement is valid for all deliveries.

The product complies with the Ph. Eur. General Text 5.2.8: Minimising the risk of transmitting animal spongiform encephalopathy agents via human and veterinary medicinal products. The General Text is identical with the Note for guidance EMA/410/01 rev. 3, published in the Official Journal of the European Union (2011/C 73/01).

- With reference to Ph. Eur. General Text 5.2.8:
 In the light of the current scientific knowledge and irrespective of the geographical origin, bovine milk is
- unlikely to present any risk of TSE/BSE contamination.

 The mentioned conditions regarding bovine milk derivatives are fulfilled and therefore, the products are unlikely to present any TSE/BSE risk and shall therefore be considered compliant with the Note for

The milk is sourced from healthy animals in the same conditions as milk collected for human consumption.

For production site Molkerei MEGGLE Wasserburg GmbH & Co.KG, Wasserburg, Germany: The sourcing of the milk is constantly, officially supervised according to EC Hygiene Regulations (EC) No 852/2004 and (EC) No 853/2004. Besides milk, no other ruminant materials with the exception of calf rennet and (EC) No 853/2004. Besides milk, no other ruminant materials with the exception of cair rennet are used. The calf rennet is produced in accordance with the process described in the risk assessment report EMEA/CPMP/BWP/337/02/Public/Final performed by the Committee for Proprietary Medicinal Products (CPMP) and its Biotechnology Working Party (BWP). In accordance with Public Statement EMEA/CPMP/571/02 of February 27 2002 the TSE risk is negligible if the calf rennet is produced in accordance with the process described in this risk assessment.

For production site Davisco Foods International, Inc., Le Sueur, MN, USA; The sourcing of the milk is constantly, officially supervised according to the FDA Pasteurized Milk Ordinance 2009. Besides milk, other ruminant materials incl. calf rennet are not used.

Freundliche Grüße / Best regards

[name]

Molkerel MEGGLE Wasserburg GmbH & Co. KG * [name] * Telefon [contact]-0 * [contact] [contact] * www.meggle-group.com * Geschläftsführung MEGGLE Wasserburg Verwaltungs GmbH vertreten durch:

DS: SII [name] MBA (Vorsitzender), [name] * [name] * [name]

Amtsgericht Traunstein HRA 7828 * USK-IdNr: CDE 81349752 * Sk-Nr. 156/116/00116

Confidential Page 65 of 22

Version 1.4 10th April 2020

Mic BloPolymer
Pharmaceutical
[name]
Page 1 PMC
[contact]
Page 2009
[contact]
Page [name]

BSE / TSE- FMC Products

Please let this letter certify that the following products manufactured by FMC Biopolymer, do not contain any raw materials produced from Animal or Human derived origin nor come into contact with Animal or Human derived materials during manufacture;

- · Avicel PH Grades (Microcrystalline Cellulose)
- Avicel RC & CL Grades (Microcrystalline Cellulose and Carboxymethylcellulose)
- Aquacoat (Aqueous Ethylcellulose Dispersion)
- · Ac-Di-Sol (Croscarmellose Sodium)

This statistical analysis plan (SAP), which is based on protocol Version 1.2 dated August 1, 2019, defines the methods and analyses that Imperial College London plans to use to analyze the data from the Self-Assessment Method for Statin side effects Or Nocebo trial (henceforth, SAMSON). This study adheres to the principles outlined in the Medicines for Human Use (Clinical Trials) Regulations 2004 (SI 2004/1031), amended regulations (SI 2006/1928), and the International Conference on Harmonisation Good Clinical Practice (ICH GCP) guidelines. It is being conducted in compliance with the protocol, the Data Protection Act, and other regulatory requirements as appropriate. If the protocol is subsequently amended, this SAP may be amended as well. Should the SAP and the protocol be inconsistent with respect to the planned analyses, the language of the SAP is governing.

2. Investigational plan

2.1. Study design

SAMSON is a randomized controlled trial evaluating in a cohort of participants the proportion of adverse symptoms truly due to the effect of statin rather than nocebo. The investigators plan to randomize participants to receive, in a random predefined order, the study interventions. Each participant will receive 12 sets of pre-labelled HDPE containers. Four sets of containers will contain no medication; four will contain a one-month supply of matched placebo; and four will contain a one-month supply of atorvastatin 20mg. At the start of the next calendar month after the screening visit, the participants will commence the trial intervention. The research nurse will call participants to remind them to start on the first day of the next month after screening; thereafter, the participants will receive a monthly reminder to switch to the next set of HDPE containers. Each day participants will rate their daily symptom on a phone application; they will complete three additional questionnaires each month.

2.2. Study objectives and outcome measures

Front-line clinicians cannot currently test whether symptoms an individual participant experiences are the pharmacological result of a statin or due to other phenomena (e.g., nocebo). The value of such a tool would be two fold:

- The tool would allow individual participants to establish for themselves whether they truly suffered a side effect from the drug or are victims of nocebo – which may in fact be more common.
- By separating the components, the tool would permit clinical researchers to explore the determinants of each, opening opportunities to obtain better clinical outcomes.

The main objectives of this study are to the following:

- To develop a method for determining for an individual participant what extent experienced symptoms are associated with the statin or merely reflect a nocebo effect.
- In a cohort of participants who have stopped statins because of adverse symptoms, to evaluate in what proportion the symptoms are truly due to the statin.

2.3. Study hypotheses

The study aims to test the following hypotheses:

- Hypothesis 1: More than 30% of participants enrolling into the study will complete it.
- **Hypothesis 2:** Overall, more than 50% of symptom burden is nocebo rather than pharmacological.

The effect of nocebo effect on side effects will be defined as:

$$\text{Nocebo effect} = \frac{\text{Nocebo component}}{\text{Total side effect (Pharmacological+Psychological)}} = \frac{(\text{average symptoms score on placebo} - \text{average symptom score on no medication})}{(\text{average symptom score on statin} - \text{average symptom score on no medication})}$$

- **Hypothesis 3:** At six months after completion of the study, at least 50% of participants will either be taking statins or have declined statins for reasons other than perceived side effects.

2.4. Randomization

Eligible participants are enrolled on InForm, which allocates each participant a random predefined order during which to take the study interventions. The Imperial Clinical Trials Unit (ICTU) generates these random codes and supplies them to the production pharmacy.

3. Study schedule

3.1. Study days

Potential participants attend a screening visit during which the study doctor receives written informed consent from those who decide to participate. The study doctor then assesses the participants' eligibility for the study by evaluating their past medical history and previous statin intolerance. Participants' blood pressure is measured. Participants who do not have a recent lipid profile recorded in the last 6-months are offered the option of having one undertaken as part of the screening visit. The study doctor determines if the participant is suitable to be enrolled in the study. Suitable participants are enrolled on InForm.

Scheduled follow-up telephone calls are undertaken each month during the 12-month period of the trial. The study nurse monitors the participants' scores. If the scores show severe discomfort or if participants are not scoring on their phone, the study nurse makes unscheduled telephone follow-up calls and, if required, arranges an unscheduled study visit to see the study doctor who performs unscheduled tests deemed necessary.

The end of study will be defined to occur when the specified number of participants have been recruited, all participants have completed the 18-month phone interview, and the database is locked.

The 12-month follow-up contact may be combined with the end of study visit; if so this would be a face-to-face visit at the study center. If so, the month 12 visit must be completed before the scheduled unblinding. The end of study visit may take place up to 31 days after the 12-month telephone follow-up. The Exhibit presents the study visit schedule

SAMSON STATISTICAL ANALYSIS PLAN

January 14, 2020

Page 4

Exhibit. Visit schedule

	D1	M1	M2	M3	M4	M5	M6	M7	M8	M9	M10	M11	M12	M18
	Screening and Enrollment	Telephone follow-up	End of Study Visit	6-month Follow-up visit										
Informed consent	X													
Inclusion/exclusion	X													
Demography	X													
Medical history	X													
Blood pressure	X													
Lipid profile (optional)	X													
Interview	X	X	X	X	X	X	X	X	X	X	X	X	X	X
EuroQol	X	X	X	X	X	X	X	X	X	X	X	X	X	X
TSQM	X	X	X	X	X	X	X	X	X	X	X	X	X	X
Confounding life events questionnaire	X	X	X	X	X	X	X	X	X	X	X	X	X	X

3.2. Unscheduled visits

Unscheduled assessments are not performed unless participants develop adverse events that the chief investigator considers 'related' to the trial procedure or to atorvastatin therapy.

4. Sample size determination and power calculation**4.1. Sample size calculation – Hypothesis 2**

Each "effect of nocebo" will be a value which, for the sake of the calculation in the protocol, was assumed to be between 0 and 1. The study aims to report an average effect of nocebo for

the population that has a 95% CI of $\pm 10\%$. To achieve this, assuming a conservative scenario of individual-participant values scattered uniformly from 0 to 1 (i.e., $SD = 1/\sqrt{12} = 0.29$), the number of participants to be studied will need to be $\geq N$ where $0.29/\sqrt{N} \leq 0.10/1.96$ (i.e., $N > (1.96 \times 0.29/0.10)^2 = 36$). The investigators planned to recruit 50 participants. In all a total of 62 participants were screened and 60 were randomized.

5. Statistical analysis: general considerations and conventions

Descriptive and inferential statistics will be used to summarize results of the SAMSON study. Continuous variables will be summarized using the number of subjects (N), mean, SD, median, 25th and 75th percentiles, and minimum and maximum. Discrete variables will be summarized using counts and percentages.

Summaries will be provided for demographics, medical history, concomitant medications, and adverse events. For summaries of medical history, concomitant medications, and AEs, the Medical Dictionary for Regulatory Activities (MedDRA®) and the World Health Organization Drug dictionaries, as appropriate, will be used.

All data listings, summaries, and statistical analyses will be generated using SAS® Version 9.4 (or higher) or other validated software.

6. Efficacy analysis

As described in Section 2.3, the study has three hypotheses.

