8 STATISTICAL AND DATA ANALYSIS

Our study's principal hypotheses will be tested as follows:

Hypothesis 1 will be tested by calculating the proportion of respondents completing the study, and the corresponding 95% confidence interval for this estimate, and examining whether the confidence interval lies completely above a value of 0.3 or not.

To test **Hypothesis 2**, comparisons between the average monthly symptom burden (measured by the monthly aggregate of symptom scores) resulting from no treatment/placebo/statin treatment periods will be made using a longitudinal multilevel model. The most basic model to test hypothesis 2 would be:

To test **Hypothesis 2**, we will calculate the nocebo ratio across all patients. This is to avoids attempting to analyse the pathological distributions that would arise for patient whose mean statin symptom score is close or less than their no treatment score, because the nocebo ratio becomes disruptively extreme. Combining the data

Confidential Page 14 of 22

SAMSON Protocol No: 1.4

Version 1.4 10th April 2020

across all patients to yield a single statin, placebo and no treatment symptom score allows a representative and interpretable nocebo ratio to be provided.

Hypothesis 3 is that the majority of patients will be taking statins, or have a non-side effect reasons for not doing so, at 6 months after study completion. This will be a descriptive statistic of the sample, which does not require inference of the population mean. No further statistical analysis is therefore necessary

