8.1 POWER CALCULATIONS

Hypothesis 1: We hypothesise that of the patients enrolling for the study, 50% or more will complete the study. Our intention is to report the proportion of patients completing the study and its 95% confidence interval. Based on the binomial principle, $SE_p = \sqrt{p \cdot q/n}$, the number of patients planned after the calculation below (50) will permit this proportion to be stated with a 95% confidence interval of $\pm 1.96\sqrt{\frac{1}{2} \cdot \frac{1}{2}/50}$. Thus the proportion will be reported with a margin of error of $\pm 14\%$

or smaller. If the long-run proportion of patients who would finish the study is ~70%, then a sample size of 50 gives 85% power to detect this at the 5% significance level.

Hypotheses 2 and 3: These hypotheses address the sample of participants and not the population at large. They therefore do not need a sample size calculations.

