$$3) \text{ Cov}(numerator, denominator) = \text{cov}(\bar{x}_p - \bar{x}_0, \bar{x}_s - \bar{x}_0) = \text{cov}(\bar{x}_p, \bar{x}_s) - \text{cov}(\bar{x}_p, \bar{x}_0) - \text{cov}(\bar{x}_0, \bar{x}_s) + \text{cov}(\bar{x}_0, \bar{x}_0) = \text{cov}(\bar{x}_p, \bar{x}_s) - \text{cov}(\bar{x}_p, \bar{x}_0) - \text{cov}(\bar{x}_0, \bar{x}_s) + s_0^2$$

$$\text{where, for example, } \text{cov}(\bar{x}_p, \bar{x}_s) = \frac{\sum_{j=1}^4 (x_{p_j} - \bar{x}_p)(x_{s_j} - \bar{x}_s)}{4 - 1}$$

$$4) s_n^2 = \text{Var}\left(\frac{\bar{x}_p - \bar{x}_0}{\bar{x}_s - \bar{x}_0}\right) = \left(\frac{\bar{x}_p - \bar{x}_0}{\bar{x}_s - \bar{x}_0}\right)^2 \left(\frac{\text{Var}(\bar{x}_p - \bar{x}_0)}{(\bar{x}_p - \bar{x}_0)^2} + \frac{\text{Var}(\bar{x}_s - \bar{x}_0)}{(\bar{x}_s - \bar{x}_0)^2} - 2 \frac{\text{cov}(\bar{x}_p - \bar{x}_0, \bar{x}_s - \bar{x}_0)}{(\bar{x}_p - \bar{x}_0)(\bar{x}_s - \bar{x}_0)}\right)$$

s = standard deviation, s² = variance, r = correlation

The Taylor's series approximation is based on asymptotic theory. Should the data not allow stable estimates of the components of the variance, we will use a bootstrapped estimate of the variance.

To calculate the 95% CI for the mean nocebo effect, the test statistic is $t = \sqrt{N}(\mu - \mu_0)/\sqrt{s^2}$

The null hypothesis is rejected if $t > t_{\alpha, N-1}$ where, in SAS, $t_{\alpha, N-1}$ is TINV(1- α , N-1);

In SAS, the p value associated with the test statistic T is PVAL=1-probt(abs(T), N-1) or PVAL=cdf('T', T, N-1).

The 95% confidence interval is $\text{Mean nocebo effect} \pm t_{\alpha/2, N-1} \sqrt{s^2} / \sqrt{N}$

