6.1.1. Missing and partial data for primary outcome

For the calculation of mean symptom score for particular treatment (statin, placebo, no medication) missing scores ($i < 28$) will be handled by only using study months that have at least 10 of daily symptom scores non-missing. We will perform sensitivity analyses using different thresholds for non-missing scores (such as 14 and 16 non-missing scores) and compare the percentage of missing symptoms scores during the 'pill' months (statin or placebo) versus 'no pill' months. We will assess the temporal pattern of missing symptom scores by comparing the percentage of missing scores at the beginning of the study to the percentages at later study months.

The nocebo effect for an individual participant will be calculated only if he or she has non-missing symptom scores for at least one month of each treatment ($j \geq 1$). If the participant has not recorded any symptom score for one of the three treatments ($j=0$ for statin, placebo, or no pill) the nocebo effect cannot be calculated, and the primary endpoint analysis will exclude that participant.

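### SAP 4.1 prints 36 where its own expression gives 32.3 (N ≥ 33), calls the assumed scatter conservative without support, and protocol 8.1 points to a derivation of 50 that does not follow

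*SAP*

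**What the plan says.** SAP 4.1 (Sample size calculation – Hypothesis 2) wants the average nocebo effect for the population to be reported with a 95% confidence interval of ±10%. Each participant's value "for the sake of the calculation in the protocol, was assumed to be between 0 and 1". The SD comes from "assuming a conservative scenario of individual-participant values scattered uniformly from 0 to 1", that is 1/√12, rounded to 0.29. The requirement is 0.29/√N ≤ 0.10/1.96, and the printed solution is that N must exceed (1.96 × 0.29/0.10)², given as 36. The section adds that 50 were planned and 60 randomised.

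SAP 6.1 averages the individual ratios (placebo minus no medication, over statin minus no medication). Its interval uses a t quantile and a variance built from within-participant variances. If those are unstable, "we will use a bootstrapped estimate of the variance". Under SAP 6.1.1, a participant with no recorded scores for one of the three treatments is left out: "the nocebo effect cannot be calculated, and the primary endpoint analysis will exclude that participant".

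Protocol v1.4, section 8.1, refers under Hypothesis 1 to "the number of patients planned after the calculation below (50"). Of Hypotheses 2 and 3 it says: "They therefore do not need a sample size calculations". Section 8 of the same protocol pools the data over patients instead of averaging individual ratios, "because the nocebo ratio becomes disruptively extreme" when a patient's statin score is near or below the no-treatment score.

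**The concern.** SAP 4.1 is the only sample-size justification given for the primary outcome. Three things in it, or tied to it, do not hold up when checked.

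- The printed result does not follow from the printed inputs.
- The word *conservative* tells the reader that the true precision should be at least as good as ±10%. No reason is given, and the quantity actually averaged can fall outside the range on which the SD is based.
- Protocol 8.1 points forward to a calculation that should explain the number 50. It then says that the primary hypothesis needs no sample size calculation, because it concerns the sample and not the population. SAP 4.1 gives such a calculation, with the population as its target.

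What is at stake is the credibility of the stated precision. The number of participants enrolled is not in question.

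**Working it through.** **Inputs, all from SAP 4.1.** Half-width h = 0.10; z = 1.96; SD = 1/√12 = 0.2887, rounded to 0.29; 50 planned; 60 randomised.

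**Step 1: the printed figure.** N ≥ (z × SD/h)².

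- With SD 0.29: (1.96 × 0.29/0.10)² = 5.684² = 32.31, so N ≥ 33.
- With unrounded 1/√12: 32.01, so N ≥ 33.
- The printed 36 is not reproduced. At z = 1.96 it would need SD = 0.10 × √36/1.96 = 0.306.
- Two routes do lead to 36: z = 2 with SD 0.30 gives (2 × 0.30/0.10)² = 36, and a 10% loss gives 32.31/0.90 = 35.9. The SAP states neither.

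**Step 2: effect on the trial at the SAP's own SD.** Half-width = 1.96 × 0.29/√N.

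- N = 50: 0.080. N = 60: 0.073.
- Since 33 analysed are enough, 50 − 33 = 17 of 50, or 60 − 33 = 27 of 60, could be excluded under SAP 6.1.1 with ±0.10 still met.

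**Step 3: how large the SD may be.** Largest SD = h × √N/1.96.

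- N = 50: 0.10 × 7.071/1.96 = 0.361, or 0.36 rounded down.
- N = 60: 0.10 × 7.746/1.96 = 0.395, or 0.39 rounded down.

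**Step 4: is the uniform a worst case on 0 to 1?**

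| Shape on 0 to 1 | SD | N needed | Half-width, N = 33 | N = 50 | N = 60 |
|---|---|---|---|---|---|
| Uniform | 0.29 | 33 | 0.099 | 0.080 | 0.073 |
| Widest single-peaked | 1/3 | 43 | 0.114 | 0.092 | 0.084 |
| Half at 0, half at 1 | 0.5 | 97 | 0.171 | 0.139 | 0.127 |

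The middle row is two-thirds uniform and one-third at an endpoint, say 1. Its mean is 2/3 × 1/2 + 1/3 = 2/3 and its mean square is 2/3 × 1/3 + 1/3 = 5/9. The variance is therefore 5/9 − 4/9 = 1/9. The uniform is the widest symmetric single-peaked shape, but not the widest single-peaked shape, and not the widest shape.

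**Step 5: does the 0 to 1 range hold?** When the statin score exceeds the no-medication score, the ratio in SAP 6.1 is above 1 if placebo scores exceed statin scores, and negative if placebo scores fall below no-medication scores. It grows without limit as the denominator nears zero. SAP 6.1.1 removes participants only for missing scores, so such ratios stay in. The documents give no SD for them, so the actual half-width cannot be computed.

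**Step 6: protocol 8.1.** After the forward reference come the margin 1.96 × √(½ × ½/50) = 0.139, reported as ±14%, and a statement that 50 participants give 85% power if about 70% would finish. Both belong to Hypothesis 1 and both start from n = 50, so neither derives it. The statement that Hypotheses 2 and 3 need no calculation comes next, and then section 9.

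**The case against.** Much can be said for the plan, and most of it stands.

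- *The slip is harmless.* True. 36 exceeds 33, and both 50 and 60 exceed 36.
- *The 0 to 1 range is openly labelled an assumption, and within it the uniform is a reasonable choice.* Also largely true. Every single-peaked shape on 0 to 1 has an SD of at most 1/3, which gives ±9.2% with 50 analysed. Disclosing the range does not make it conservative, however. At the minimum N of 33, or even at 36 (1.96 × (1/3)/6 = 0.109), a single-peaked shape can miss the target.
- *Protocol 8.1 does contain a calculation at n = 50.* It does, so it would be wrong to say that nothing follows the forward reference. What is missing is a derivation of 50.
- *The SAP rests on another version of the protocol* ("which is based on protocol Version 1.2 dated August 1, 2019"). That version was not available for this review and may have held the derivation. The SAP's own mention of a protocol calculation is therefore not called wrong here.
- *The SAP governs where it and the protocol differ.* That rule concerns planned analyses. It does not correct a sum or supply a derivation.

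A reader might infer that the minimum should be 35, because SAP 6.1 uses a t quantile. With SD 0.29, t does give 35. But SAP 4.1 uses 1.96, and the SAP 6.1 interval also has a different variance, so putting t alone into section 4.1 would describe neither.

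**Conclusion.** Minor, and wrong as written. The printed 36 should be 32.3, so at least 33 participants analysed; the error of 3 is in the safe direction. *Conservative* is unsupported. The ±10% depends on the 0 to 1 assumption and on a between-participant SD of at most about 0.36 with 50 analysed, or 0.39 with 60. Protocol 8.1 points to a derivation of 50 that v1.4 does not contain, and its statement that Hypothesis 2 needs no calculation does not fit SAP 4.1.

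These figures rest on the form SAP 4.1 itself uses (SD/√N with z = 1.96). They do not describe the interval in SAP 6.1.

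Three stronger readings are not supported:

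- **The trial is too small.** At the SAP's SD, both 50 and 60 give better than ±10%, provided that at least 33 are analysed.
- **The precision is really about ±13.9%.** That needs half the participants at exactly 0 and half at exactly 1, which nothing in the documents suggests.
- **The ratios are known to be too variable for ±10%.** Protocol section 8 says that individual ratios can be extreme, but the documents contain no SD for them.

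**What to change.** **SAP 4.1.** Change the end of the expression to '(1.96 × 0.29/0.10)² = 32.3, so N ≥ 33 participants analysed'. Replacing 36 by 33 alone would print another false equality. Delete *conservative*. Add that the ±10% is conditional on the between-participant SD of the individual ratios being at most about 0.36 with 50 analysed (0.39 with 60).

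**Protocol 8.1.** Either delete the clause that points forward to a calculation, or restore the derivation of 50. Then reconcile the statement that Hypothesis 2 needs no sample size calculation with SAP 4.1, which gives one.

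**Cost.** Wording in two documents, with no change to enrolment, data collection or analysis. The one downside is that the stated precision becomes explicitly conditional on an SD that the documents do not give.
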